2.9. Measuring the effectiveness of rehabilitation

To test hypothesis I., i.e., a positive influence on all outcomes, the effect of therapy for each therapeutic group will be assessed separately by paired t-tests performed on pre-test and post-test scores. The Wilcoxon rank test will be used on data where normal distribution cannot be expected.

To test hypotheses II. and III, a comparison between therapeutic groups will be performed using two sample Student t-tests on differences between measurement time points (or Wilcoxon tests respectively for data, where normal distribution of the differences cannot be expected). For hypothesis II, the COMIRESTROKE - ICF group will be compared against the rest of the participants. For hypothesis III, the COMIRESTROKE - NEFI group will be compared against the rest of the participants. A one-sided alternative will be tested according to our hypotheses. We will also implement the one-way ANOVA test to jointly compare all three groups for prepost differences. In addition, a Tukey post-hoc comparison will be made to detect any further group differences beyond our hypotheses.

To assess the overall impact of rehabilitation and to compare effectiveness of different therapeutic approaches for Hypotheses I – III in more complex way, and to test for effect of other covariates in Hypothesis IV, a linear mixed effect model will be used with random patient effect fitted to longitudinal patient data. Measurement effect, group effect and their interaction, as well as effects of other covariates such as the level of disability in admission time will be tested by F test.

To address Goal I, correlations between changes in different examination scores will be evaluated using Pearson correlation coefficient and its nonparametric analogies. A cluster analysis will be performed to identify different phenotypes. This will allow the identification of different groups of patients in relation to the efficacy of the neuro-rehabilitation programs.

To address Goal II, for selected multi-item instruments, item-response theory (IRT) and generalized linear regression models will be used to study differential item functioning with respect to rehabilitation groups. Account will be taken for other respondent characteristics. Use will be made of differential item functioning in change (DIF-C) analysis (7) in order to detect between-group differences.

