2.1. Clinical trial design

This will be a Four-Arm Parallel-Group Randomised Double Blinded Controlled Trial with a longitudinal design. Patients who fulfilled inclusion criteria will be randomly assigned to one of the four research groups (Group 1, 2, 3 or 4). Three groups will undergo an inpatient COMIRESTROKE (4 hours/day for 3 weeks). Group 1 (COMIRESTROKE – ICF) will undergo individualised rehabilitation therapy embodying the ICF system as a therapeutic tool, where current needs and wishes of the person after IS are integrated into an interdisciplinary team rehabilitation programme management. Group 2 and 3 will undergo a standard comprehensive intensive rehabilitation program three hours per day (39) plus one hour of specific PT (an individual neuroproprioceptive "facilitation inhibition" for Group 2, a technology-based training for Group 3). Group 4 will undergo standard care and will serve as comparative one to the intensified intervention groups.

Participants will be examined four times (Figure 1). At the beginning and after three weeks of hospitalization (both primary, secondary outcomes and a blood draw will be obtained for total RNA extraction, cDNA synthesis and real-time QPCR assessment of lncRNA candidates previously identified as potential therapeutic influencers in ischemic stroke), and then three months and one year after the end of the program (primary outcomes only).

Figure 1: Design of the study

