2.2. Eligibility criteria and subgroups

Participants will be identified by specialists in neurology and rehabilitation from inpatients at the Department of Acute Care, Department of Neurology, Thomayer University Hospital or University Hospital Kralovske Vinohrady, Prague, Czech Republic.

Inclusion criteria: Adults (18 - 85 years) after the first ischemic stroke in early sub-acute phase (40, 41), with a slight to moderately severe disability [2 - 4 on the Modified Rankin Scale (42)],

with minimal or moderate motor deficit of upper or lower extremities (on NIHSS Item 5 or 6 scores 1–3 points) who were able to perform activities of daily living prior to stroke event [0 – 2 on the Pre-Stroke Modified Rankin Score (43)], with a potential to accept 4 hours of comprehensive rehabilitation per day and to profit from the physiotherapy. Czech is their native language or its knowledge is at the level of the mother tongue.

Exclusion criteria: Low level of consciousness (vegetative state and/or minimally conscious state); severe cognitive decline that would interfere with administration of the tests, premorbid illiteracy, severe visual and/or auditory deficit that would prevent proper completion of the tests; behavioural disorders and/or lack of cooperation with therapist; and severe medical problems with a poor prognosis, (e.g., severe frailty, advanced and incurable cancer, fracture, cardiovascular disorders as chronic heart failure NYHA III, IV, symptomatic coronary artery disease Angina Severity Class III, IV, respiratory insufficiency as chronic obstructive pulmonary disease GOLD IV, and other severe disease) (44).

Randomisation

All patients meeting the above criteria will be invited to participate and asked to provide a written informed consent. They will be randomly assigned (1:1:1:1) as soon as possible, but always within 48 hours of admission, into one of the four interventions (represented by Group 1, 2, 3 or 4) using offsite-independent randomization protocols (www.randomization.com). Concealed allocation will be performed using sequentially numbered opaque sealed envelopes only accessible by research personnel with no involvement in the trial.

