2.6. Estimated size

It is estimated that approximately 110 people will be recruited to the clinical trial each year. This number is based on the fulfilment of performance and quality indicators report of cerebrovascular care at the Centre for Highly Specialized Patient Care for Stroke Patients at Thomayer Hospital 2019. A total of 210 people is expected to be enrolled in the clinical trial over a period of two years (Figure 2), corresponding to a required sample number of 70 patients per group. This value is necessary in order to detect a significant difference in improvement

between two groups when achieving a mean difference effect (Cohen's d = 0.5), a significance level of $\alpha = .05$ and a strength of $1-\beta = .80$. The sample size was determined based on the minimal clinically significant change on a Berg balance scale (96).

Figure 2: Planned recruitment and randomisation process

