2.8. Hypotheses

This clinical trial will test the following scientific hypotheses:

I. COMIRESTROKE under all three settings has a positive influence on all outcomes and higher effect than control group.

II. COMIRESTROKE - ICF will have the highest impact on primary outcomes (GAS, PROMIS, WHODAS 2.0) and on such secondary outcomes that were identified as treatment goals. Furthermore, we expect the highest impact on the primary outcomes in the follow-up (three and twelve months after finishing the rehabilitation).

III. COMIRESTROKE – NEFI will have the highest effect on the secondary outcomes, mainly on motor functions. Moreover, it will most significantly lead to the initiation of plastic and adaptive processes, assessed by the level of lncRNAs in the peripheral blood.

IV. The most important predictor of effective rehabilitation will be the level of disability at admission time; however, the content of the rehabilitation will have an impact on perceived, clinical, and physiological changes of the rehabilitant.

The exploratory goals of this clinical trial are as follows:

Goal I - Improvement patterns: Considering the high number of measured outcomes, for a deeper understanding of therapy efficacy with respect to patient and treatment characteristics, this clinical trial will aim to identify groups of patients with similar improvement patterns post therapy.

Goal II - Item-level analysis: To provide a deeper understanding of the differences in effectiveness between the three therapeutic approaches, this clinical trial will plan to explore item-level between-group differences in improvement.

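### Hypothesis I is tested by uncontrolled paired t-tests within each programme, with no contrast against Group 4 named, so natural recovery can be reported as a therapy effect

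*Combined protocol and SAP*

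**What the plan says.** Section 2.8 gives Hypothesis I two halves: "COMIRESTROKE under all three settings has a positive influence on all outcomes and higher effect than control group". Section 2.1 gives the fourth arm its role: "Group 4 will undergo standard care and will serve as comparative one to the intensified intervention groups".

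Section 2.9 restates Hypothesis I as the first half only and names its test: "the effect of therapy for each therapeutic group will be assessed separately by paired t-tests performed on pre-test and post-test scores", with a Wilcoxon test where normality is doubtful. The other analyses in section 2.9 are:

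- **Two-sample tests** on change for Hypotheses II and III. These set the ICF arm, and then the NEFI arm, against everyone else pooled.
- **One-way ANOVA**: "We will also implement the one-way ANOVA test to jointly compare all three groups", on pre-post differences.
- **Tukey comparisons**: "a Tukey post-hoc comparison will be made to detect any further group differences beyond our hypotheses".
- **A linear mixed model** for Hypotheses I to III, with F tests of "Measurement effect, group effect and their interaction" and of covariates.

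No section names a contrast of any programme with Group 4.

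**The concern.** The patients are enrolled "after the first ischemic stroke in early sub-acute phase", and the Discussion (section 3) itself says that recovery in this phase is partly spontaneous. A change from baseline within one arm is the sum of spontaneous recovery, other care and any effect of the programme. A paired test shows only that the sum is not zero, yet the plan calls it the effect of therapy.

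Hypothesis I is the only hypothesis that names the control group, and the half that needs it has no stated deciding test. As written, the plan lets a positive influence be declared for all three programmes when none does better than standard care. The choice between paired tests, an overall F test and unplanned contrasts would then be made with the data in view.

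**Working it through.** **1. Inputs.** Section 2.6 gives d = 0.5, alpha 0.05, power 0.80, 210 patients in total, "corresponding to a required sample number of 70 patients per group". Section 2.2 gives four arms at 1:1:1:1.

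**2. The plan's own figure.** The normal approximation gives n = 2(1.96 + 0.842)²/0.5² = 62.8, so 63 per group two-sided; the exact t-test gives 64. One-sided, the figures are 50 and 51. The stated 70 is not reproduced unless an unstated dropout allowance is added (63/0.90 = 70, or 64/0.92 = 69.6). Also, 3 × 70 = 210, but four equal arms give 210/4 = 52.5. This is a separate issue; results below are shown for both 52 and 70 per arm.

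**3. Assumptions.** Change scores are normal with SD 1 and equal variances. Data are complete, arms are independent, there is one outcome, and recovery is the same in all four arms. The documents give no recovery size, so δ (in SD of change) is varied.

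**4. Paired test when therapy does nothing.** The probability of significant improvement in one arm is P(T > t₀.₉₇₅,ₙ₋₁), where T is noncentral t with n − 1 df and noncentrality δ√n. For n = 52 and δ = 0.5, the noncentrality is 0.5 × 7.211 = 3.606 and the critical value is 2.008, giving 0.943. For three independent arms, cube it: 0.943³ = 0.84.

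| Recovery δ | One arm, n = 52 | All three, n = 52 | One arm, n = 70 | All three, n = 70 |
|---|---|---|---|---|
| 0.2 | 0.29 | 0.025 | 0.38 | 0.054 |
| 0.3 | 0.56 | 0.18 | 0.70 | 0.34 |
| 0.5 | 0.94 | 0.84 | 0.985 | 0.96 |
| 0.8 | >0.999 | >0.999 | >0.999 | >0.999 |

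Simulation (40,000 trials) agrees for δ from 0.3 to 0.8. In the same trials, a two-sided 5% test of one programme against Group 4 falsely favoured the programme in about 2.5% at every recovery size. All three contrasts did so together in about 0.2%.

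**5. Do the other analyses supply the contrast?**

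- The two-sample tests mix Group 4 with two active programmes. They belong to Hypotheses II and III, and the TECH arm has none.
- An ANOVA of the three programmes cannot see a benefit they share. If all three beat Group 4 by 0.5 SD, it rejects in about 5% of trials.
- The Tukey comparisons are placed outside the hypotheses by their own wording.
- The mixed-model interaction is a controlled test if Group 4 is in the model, but one effective programme is enough to make it significant.

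**6. The interaction when only one programme works.** Simulation of 20,000 trials: recovery 0.5 SD, one programme +0.5 SD, the other two equal to control, four-arm F test on change with 3 and 4n − 4 df.

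| Result | n = 52 | n = 70 |
|---|---|---|
| Interaction F significant | 0.74 | 0.86 |
| F and all three paired tests significant | 0.63 | 0.84 |
| All three contrasts with Group 4 significant | 0.005 | 0.006 |

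The plan's two analyses of Hypothesis I would often both be positive although two of the three programmes equal standard care.

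**7. Power of the controlled test at d = 0.5.** The noncentrality is d√(n/2). For n = 52 it is 0.5 × √26 = 2.550, with critical value 1.983, giving power 0.714. For n = 53 power is 0.722, and for n = 70 it is 0.836. All three contrasts together reach 0.49 with 52 per arm and 0.67 with 70.

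**The case against.** The strongest reply is that section 2.9 does tie a controlled analysis to Hypothesis I. Nothing excludes Group 4 from the mixed model, and its group-by-measurement interaction would then be a randomised comparison. With no therapy effect and recovery of 0.5 SD, that F test is significant in about 5% of trials, and together with all three paired tests in only about 2% (52 per arm) to 4% (70). Read jointly, the two analyses would control the error when no programme works. This stands, and the 0.84 applies only if the paired tests are read alone. But the plan does not require a joint reading, does not say that the model overrides the paired tests, and names no contrast. A joint reading also fails when one programme works (step 6).

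Three smaller points also stand as limits on size:

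- With recovery of 0.1 or 0.2 SD, all three paired tests are rarely significant together (about 0.001 and 0.025 at 52 per arm).
- The figures are for one outcome. If three primary outcomes were independent, 0.84 would become 0.84³ = 0.59; positive correlation would raise it.
- Paired tests alone cannot establish the full wording of Hypothesis I, because its second half requires superiority to control. That half, however, is the one left without a deciding test.

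The reference to three groups in the ANOVA may be left over from a three-arm design, since 210 is 3 × 70. A four-group ANOVA with Tukey would yield every comparison with Group 4. That is an inference, and the plan still places those comparisons outside its hypotheses.

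**Conclusion.** The concern holds, and the plan is wrong as written on this point. The test that section 2.9 names for Hypothesis I ignores the randomised control, and no other planned analysis is designated to compare each programme with Group 4.

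The size depends on natural recovery, which the documents do not quantify. Under the assumptions in step 3, the chance that all three ineffective programmes show a significant paired change ranges from 0.025 (0.2 SD, 52 per arm) to above 0.999 (0.8 SD). Already at 0.3 SD, each paired test is significant more often than not. The mixed model reduces the problem but does not remove it. If one programme works, the overall F test and all three paired tests are positive together in 63% (52 per arm) or 84% (70) of trials, against under 1% for all three contrasts with Group 4.

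**What to change.** In section 2.9:

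- State that Group 4 is included in the mixed model.
- Make the deciding test of Hypothesis I the pre-specified contrast of each programme with Group 4 on change from baseline (a group-by-time contrast in the mixed model, or ANCOVA). Apply it at three weeks and, for the primary outcomes, at follow-up.
- If the claim is that all three programmes beat control, require each of the three contrasts to be significant at alpha, with no adjustment across them. If separate claims per programme are intended, use a Dunnett-type adjustment. A single contrast of the pooled programmes with Group 4 has more power (about 0.88 at 52.5 per arm, d = 0.5) but answers only the average claim.
- Keep the paired tests as description and report them for Group 4 as well.

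The change is to wording only and needs no new data. Its cost is a test less likely to be significant. At d = 0.5, two-sided 0.05, power per contrast is 71–72% with 52–53 per arm and 84% with 70. Power for all three together is about 49% and 67%, before any allowance for several outcomes, several time points or dropout. With four arms, 80% power per contrast needs 63–64 per arm (252–256 in total) before dropout.

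### Hypotheses II and III use a pooled-variance Student t-test on a 1:3 contrast, which keeps its level only if change scores are equally spread; Welch's test should be named instead

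*Combined protocol and SAP*

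**What the plan says.** Section 2.9 tests hypotheses II and III on change scores: "a comparison between therapeutic groups will be performed using two sample Student t-tests on differences between measurement time points". Under II, the contrast is stated as "the COMIRESTROKE - ICF group will be compared against the rest of the participants". The third hypothesis is handled in the same way, with NEFI as the single arm. The direction is fixed in advance: "A one-sided alternative will be tested according to our hypotheses". The only alternative test is rank-based, "or Wilcoxon tests respectively for data, where normal distribution of the differences cannot be expected", so it is triggered by non-normality and not by unequal spread.

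Section 2.2 sets the group sizes: "They will be randomly assigned (1:1:1:1) as soon as possible". Section 2.1 describes the fourth arm: "Group 4 will undergo standard care and will serve as comparative one to the intensified intervention groups". Read plainly, each comparison is therefore one arm against three, with standard care inside the pool. The ANOVA sentence in 2.9 speaks of three groups, and the total in 2.6 is 210 = 3 × 70, so a reading in which the pool holds two arms cannot be excluded.

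Section 2.9 also plans one-way ANOVA, Tukey comparisons and a linear mixed model with a random patient effect. None of these is given arm-specific variances. The .05 level appears only in section 2.6, without sidedness, and is not tied explicitly to these tests.

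**The concern.** Student's two-sample test, in its usual sense, estimates one common variance. With equal group sizes, unequal spread hardly matters, because the errors in the two halves of the standard error cancel. At 1:3 they do not. The large group dominates the pooled variance, while the small group dominates the true variance of the difference. If the single arm varies more than the pool, the standard error is too small and false claims for ICF or NEFI become more frequent. If it varies less, the test is conservative and power is lost.

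The documents do not allow equal spread to be taken for granted. In section 2.3 the time Group 1 spends with each specialist depends on individual goals, whereas Groups 2 and 3 follow a routine three-hour programme plus one added hour, and Group 4 receives standard care. These differences could move the spread either way. At stake is the error rate of the tests that section 2.9 assigns to two of the four hypotheses.

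**Working it through.** **The plan's own figure.** Section 2.6 gives 70 per group for d = 0.5, α = .05 and power .80. The normal formula n = 2(z₁₋α + z₁₋β)²/d² gives 2(1.960 + 0.842)²/0.25 = 62.8, so 63 per group two-sided (64 with the exact t), or 50 one-sided. The 70 is not reproduced without an allowance that the plan does not state. It is on the cautious side and does not affect this point.

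**Inputs**
- Arms and ratio: four, 1:1:1:1 (2.1, 2.2).
- Total: 210 (2.6). 210/4 = 52.5, so 52–53 v 157–158; I use n₁ = 52 and n₂ = 158.
- 1:2 reading (pool without Group 4): 52 v 105.
- Level: one-sided 5%, combining 2.6 and 2.9.
- SD of change by arm: not given. The ratio r = SD(single arm)/SD(pool) is an **assumption**, varied from 0.67 to 2.

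**Formula.** With the pool's SD set to 1:
- True variance of the mean difference: V = r²/n₁ + 1/n₂
- Pooled variance, in expectation: s² = [(n₁−1)r² + (n₂−1)]/(n₁+n₂−2)
- Variance the test assumes: A = s²(1/n₁ + 1/n₂)
- Actual error ≈ 1 − Φ(t₀.₉₅ / √(V/A))

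**Example, r = 1.25.**
- V = 1.5625/52 + 1/158 = 0.03638
- s² = (51 × 1.5625 + 157)/208 = 1.1379
- A = 1.1379 × 0.02556 = 0.02909
- √(V/A) = 1.118
- t₀.₉₅ with 208 df = 1.652, and 1.652/1.118 = 1.477, so the error is about 7.0%.

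**Results** (normal data, equal means, one-sided nominal 5%, 2,000,000 simulated trials per cell):

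| r | √(V/A), 52 v 158 | Formula | Student, 52 v 158 | Student, 52 v 105 | Welch, both |
|---|---|---|---|---|---|
| 0.67 | 0.823 | 2.2% | 2.3% | 3.1% | 5.0% |
| 0.8 | 0.894 | 3.2% | 3.3% | 3.8% | 5.0% |
| 1 | 1.000 | 4.9% | 5.0% | 5.0% | 5.0% |
| 1.25 | 1.118 | 7.0% | 7.0% | 6.3% | 5.0% |
| 1.5 | 1.219 | 8.8% | 8.9% | 7.4% | 5.0% |
| 2 | 1.370 | 11.4% | 11.5% | 9.0% | 5.0% |

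Smaller runs at 52 v 158 gave 7.0–7.2% at r = 1.25 and 8.8–8.9% at r = 1.5, which is simulation noise. With equal sizes (70 v 70), Student's test stays at about 5.0% throughout, so the effect needs unequal size and unequal spread together.

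**Mixing of means alone.** Suppose all arms share one SD and the three pooled arms have means (0.25, 0.25, −0.5). The pool SD is then √(1 + 0.125) = 1.06. With means (1/3, 1/3, −2/3) it is √(1 + 0.222) = 1.11. With the single-arm mean equal to the pool mean, Student's error is 3.6–4.1%, which is conservative.

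**Cost of Welch in power.** With equal SDs, 52 v 158 and a true shift of 0.4 SD, power is 80.2% for Student and 79.9% for Welch.

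**The case against.** The strongest reply is that the problem is hypothetical. The arms are randomised from one eligible population, no SD is given, and at equal spread the test is exact. Section 2.3 also says that treatment is adapted to the patient in every arm, and the TECH device is chosen by indication, so individualisation is not special to ICF. For NEFI the documents give no particular reason to expect wider spread. All of this stands, and it limits the point to a safeguard.

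A reader might infer that a more mixed pool inflates false claims. It does not: mixing alone makes the test conservative. Inflation needs the ICF or NEFI arm to vary more than the pool, which is possible but not shown. A reader might also conclude that equal spread is implausible; the documents support only that it cannot be assumed.

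Welch's test is not perfect either. At 52 v 158 with equal SDs and skewness 1, its two one-sided error rates are about 4.2% and 6.0%, against 5.1% and 4.9% for Student; at skewness 2 they are 3.6% and 6.7%, against 5.5% and 4.2%. This is a real but small cost for moderately skewed change scores.

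The ANOVA and Tukey analyses compare near-equal arms and are less exposed. They do not replace the one-sided tests, and neither they nor the mixed model allow the variance to differ by arm.

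The Wilcoxon fallback also drifts at 52 v 158 (about 3% at r = 0.5 and 9% at r = 2). A reader might want the Brunner–Munzel test in its place. That test addresses P(X<Y) = 1/2, which is not a comparison of location when data are skewed, so I do not propose it.

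**Conclusion.** The point holds as a conditional weakness. The plan names a pooled-variance test for a contrast that is 1:3 by its own allocation, and provides for unequal variance nowhere. At one-sided 5% the error stays within about 3.3–7% for SD ratios of 0.8–1.25; a ratio of 1.5 brings it close to 9%, or about 7.5% if Group 4 is outside the pool. These figures assume normal change scores, a total of 210, and SD ratios that are mine and not the plan's. They also assume that the .05 of section 2.6 is the level meant for these one-sided tests, and that Student is meant in its pooled sense.

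The documents do not show that the error rate is in fact wrong, nor in which direction. The point does not undermine the trial; it is a cheap improvement worth making before analysis.

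**What to change.** In section 2.9, replace Student's t-test for hypotheses II and III by Welch's unequal-variance t-test, and state the one-sided level. If Welch was already intended, naming it settles the matter. In the same place, state whether Group 4 belongs to the pool.

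In the mixed model, allow the residual variance to differ by arm, for example with varIdent in nlme, a library section 2.10 already plans. With only a random patient intercept, the variance of a change between two visits is twice the residual variance, so this is the term that lets spread of change differ between arms.

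The cost is about one sentence for each change. The power loss with equal variances is about 0.3 percentage points in the case worked above. For strongly skewed outcomes the small tail asymmetry of Welch's test should be borne in mind; the log transformations mentioned in section 2.7 may reduce it.

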2.7. Descriptive statistics

On the baseline, the distribution of all primary and secondary outcomes will be visualized using histograms and QQ plots. We expect normal distributions in most of the variables defined as raw scores from appropriate tests, or in their log transformations (e. g. tests measuring time needed to walk certain distance or to perform a task). The groups will be compared in their characteristics, primary, and secondary outcomes using the one-way analysis of variance (ANOVA), and its nonparametric version (Kruskal – Wallis test), where needed. The Benjamini-Hochberg correction (97) will be used to account for multiple comparisons. We expect no differences between groups on the baseline. If differences are observed, these will be accounted for in the longitudinal models.

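### Between-group tests for hypotheses II and III use raw change scores without a baseline covariate, and baseline adjustment depends on whether imbalance is seen; a prespecified ANCOVA would usually be more precise

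*Combined protocol and SAP*

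**What the plan says.** Section 2.9 tests hypotheses II and III by setting one arm (ICF or NEFI respectively) against all other participants, using "two sample Student t-tests on differences between measurement time points", with a rank-based fallback: "or Wilcoxon tests respectively for data, where normal distribution of the differences cannot be expected". On sidedness: "A one-sided alternative will be tested according to our hypotheses". Two further comparisons use the same change scores: "We will also implement the one-way ANOVA test to jointly compare all three groups for prepost differences", then "In addition, a Tukey post-hoc comparison will be made to detect any further group differences beyond our hypotheses". None of these has a baseline covariate.

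Section 2.9 also plans a linear mixed model with a random patient effect for hypotheses I to IV. Its tested terms are "Measurement effect, group effect and their interaction, as well as effects of other covariates such as the level of disability in admission time". The outcome's own baseline is not named as a covariate, and the plan does not say whether covariates enter as main effects or interact with time.

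Section 2.7 compares arms at baseline by ANOVA or Kruskal-Wallis. It states "The Benjamini-Hochberg correction (97) will be used to account for multiple comparisons" and then "If differences are observed, these will be accounted for in the longitudinal models". No threshold for an observed difference is given, and the rule does not reach the t-tests or the ANOVA.

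**The concern.** A change-score comparison is an adjusted comparison with the baseline slope forced to 1. When the true slope is below 1, as regression to the mean usually makes it, this over-corrects and adds variance that ANCOVA removes. The baseline values are already collected, so the plan gives up precision on PROMIS, WHODAS 2.0 and most secondary outcomes for nothing in return. Chance baseline imbalance is this same loss seen within a single trial, not an additional harm.

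The second issue is prespecification. Under randomisation any baseline difference is due to chance, so a rule that adjusts only when one is seen lets chance, read against an unstated cut-off, choose the model.

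**Working it through.** **Inputs.** From section 2.6: d = 0.5, alpha .05, power .80, 210 patients, 70 per group. From section 2.2: four arms, 1:1:1:1. Assumed, because the documents give neither: pre-post correlation ρ from 0.5 to 0.9, and q = SD_post/SD_pre of 1 or 1.2. I take d as standardised on the change-score SD and apply it to the one-versus-rest contrast as well.

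**The plan's own figure.** A two-sided test needs 63 (normal) or 64 (t) per group; a one-sided test needs 50 or 51. The stated 70 appears only with an unstated 8–10% dropout (64/0.92 or 63/0.90). Also, 3 × 70 = 210, whereas four arms give 210/4 = 52.5 each. That mismatch is a separate issue; I use 52.5 below.

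**Variance ratio, ANCOVA to change score, common slope.**

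General: q²(1−ρ²)/(1+q²−2ρq). With q = 1 this is (1−ρ²)/[2(1−ρ)] = (1+ρ)/2. There is no gain when ρq = 1; for example q = 1.25 and ρ = 0.8 give 1.00.

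**Power.** Noncentral t, ANCOVA effect d/√ratio, one df fewer. Tukey critical t = studentized range/√2 = 2.590 (four arms, df 206) or 2.367 (three groups). Both are shown because section 2.9 speaks of three groups while the trial has four.

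| | Change score | ρ=0.5 | 0.6 | 0.7 | 0.8 | 0.9 |
|---|---|---|---|---|---|---|
| Ratio, q=1 | 1 | 0.75 | 0.80 | 0.85 | 0.90 | 0.95 |
| One vs rest, one-sided, 52.5 vs 157.5 | 93.1% | 97.5 | 96.8 | 96.0 | 95.1 | 94.1 |
| Pairwise, two-sided, unadjusted | 71.8% | 83.4 | 81.0 | 78.6 | 76.3 | 74.0 |
| Tukey, four arms | 49.0% | 64.4 | 60.8 | 57.5 | 54.5 | 51.6 |
| Tukey, three groups | 57.8% | 72.2 | 69.0 | 66.0 | 63.1 | 60.4 |
| Ratio, q=1.2 | 1 | 0.87 | 0.92 | 0.97 | 1.00 | 0.98 |
| One vs rest, q=1.2 | 93.1% | 95.6 | 94.7 | 93.8 | 93.2 | 93.6 |
| Tukey, four arms, q=1.2 | 49.0% | 56.2 | 53.2 | 50.8 | 49.2 | 50.2 |

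**Unequal slopes (simulation, 52 vs 158).** With slope 1.0 in the single arm and 0.6 in the rest, the variance ratio is 1.06 for pooled-slope ANCOVA and 0.99 with a centred baseline-by-group term. With the slopes reversed it is 0.92 and 0.86. Under a common slope the centred term costs less than 0.01 in power. One-sided 5% error under unequal slopes was .039–.064 for change scores, .057–.060 for pooled ANCOVA and .056–.059 for the centred version. It was .052–.053 with HC2 standard errors that also include the variance of the mean baseline.

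**Does the mixed model cure it?** One simulated trial, 210 patients, two visits, complete data, random intercept; ICF-by-time estimate (SE):

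- no disability covariate: 0.2987 (0.1500)
- admission disability (mRS) as a main effect: 0.2987 (0.1500)
- raw difference in mean changes: 0.2987
- mRS-by-time term: 0.2425 (0.1473)
- ANCOVA on the outcome's own baseline: 0.3299 (0.1207)

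A main-effect covariate therefore leaves the contrast at the raw change. An interaction with time alters it but still does not supply the outcome's own baseline.

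**How often the conditional rule fires.** Four-arm ANOVA on baseline outcomes, inter-outcome correlation 0 or 0.3, 6,000 runs. If an observed difference means significance after Benjamini-Hochberg at an assumed 5%, the rule fires in 4.5–5.2% of trials, so about 95% get no adjustment from it. If it means any unadjusted p < .05 among an assumed 20–25 outcomes, it fires in 56–71%.

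**The case against.** The change-score tests are unbiased, and on the contrasts that carry hypotheses II and III the gain is about 1 to 4 percentage points from a base above 90%. The larger gains are in the Tukey comparisons, which the plan places outside its hypotheses. With q = 1.2 and ρ of 0.7 or more, the gain is below 2 points, and neither quantity is in the documents. All of this stands, and it limits the weight of the point.

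The plan also has a mixed model that lists admission disability without any condition, so those analyses need not be wholly unadjusted. That is fair, and with incomplete follow-up the exact equality with raw change would no longer hold. But the outcome's own baseline slope is still missing.

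Section 2.7 names its tests and the Benjamini-Hochberg correction, so the 56–71% reading is the less natural one. Even so, the cut-off is unstated, and the natural reading leaves the rule idle in about 95% of trials.

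Finally, ANCOVA is not uniformly better. The pooled-slope form can lose slightly in the 1:3 contrast. In a check of 1,200 runs under normality at ρ = 0.9, ANCOVA on ranks had 92.5% power against 93.5% for the Wilcoxon test on differences. These are reasons to specify the model with care, not to leave the baseline out.

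**Conclusion.** The concern holds as a matter of efficiency and prespecification, not of bias. The plan should be changed, though the trial's validity does not depend on it. The loss is modest for the one-versus-rest tests (93.1% against 94.1–97.5%) and larger for four-arm Tukey comparisons (49.0% against 51.6–64.4%). These figures assume ρ of 0.5 to 0.9, equal SDs, a common slope, 52.5 per arm and d = 0.5 on the change SD. The gain falls to almost nothing as ρ × SD_post/SD_pre approaches 1. The objection to the conditional adjustment rule does not depend on ρ.

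**What to change.** - For PROMIS, WHODAS 2.0 and each secondary outcome scored at both baseline and follow-up, prespecify ANCOVA of the follow-up score (log scale where section 2.7 expects it) on group and the baseline of the same score. Admission mRS is optional.
- Add a centred baseline-by-group term. Name the variance estimator: HC2 with the variance of the mean baseline included is the version that came closest to nominal error here.
- Take the ICF-versus-rest, NEFI-versus-rest, joint and post-hoc contrasts from this model.
- Where normality fails even after transformation, use a rank-based version, such as ANCOVA on ranks, in place of the Wilcoxon test on differences.
- For the repeated follow-ups, use a mixed model adjusted for baseline with baseline-by-visit terms, for between-group contrasts only. Keep the paired tests or the existing mixed model for the within-group effect in hypothesis I.
- Replace the conditional sentence in section 2.7 with this fixed adjustment, and present the baseline table descriptively.
- State what applies elsewhere. GAS has no described baseline score and MoCA shows no follow-up in Table 2 as extracted, so neither is covered. Say whether lncRNA levels, named in hypothesis III, follow the same model.

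Cost: no new data, about one degree of freedom per covariate or interaction term, and some extra analysis work for the robust errors, the rank fallback and a separate between-group model.
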